#### 3.3 EFFICACY/PHARMACOKINETIC MEASUREMENTS

[figure not shown]
# 3.3.1 Clinical and Laboratory Measurements for Efficacy

A detailed description and evaluation of the *Candida* infection will be performed at screening, daily while on study therapy, on the last day of study therapy, and at the 2-week and 8-week posttherapy follow-up visits. Resolution or progression of the *Candida* infection should be documented by assessment of signs and symptoms, radiographic studies (when clinically indicated), and follow-up blood cultures or, as appropriate, other follow-up cultures (including urine or CSF).

Based on all available data, an efficacy assessment will be made at the end of study therapy and at the 2-week posttherapy follow-up visit. The efficacy endpoint will be based on fungal-free survival (i.e., the proportion of patients who survived at the timepoint of interest and had documented microbiological eradication of Candida sp. from follow-up cultures collected after the initiation of study therapy). Microbiological eradication denotes negative follow-up cultures for Candida sp. from the site of infection at the time of evaluation. If a culture is not obtained on the day of assessment, then the last culture after study entry may be used to assist in the assessment of microbiological eradication. If the last culture is negative for *Candida* sp., then microbiologic eradication would be considered achieved. Although fungal-free survival will be assessed at 2 different time points (end of study therapy and the 2-week posttherapy follow-up visit), the primary efficacy time point will be at the 2-week posttherapy follow-up visit. **NOTE:** Fungal-free survival assumes no additional antifungal therapy is required for the treatment of the underlying Candida infection once study therapy has ended; however, once study therapy has ended, prophylaxis with an antifungal agent (e.g., fluconazole) may be administered, if this is deemed appropriate by the investigator.

**Protocol/Amendment No.:** 064-02

The efficacy with caspofungin in neonates and infants enrolled in this study will be compared descriptively to the efficacy in caspofungin-treated patients enrolled with invasive candidiasis in the prior Phase II pediatric documented infection study (Protocol 043, children and adolescents [3 months to 17 years]) and prior Phase III adult studies (Protocols 014 and 801).

#### 3.3.2 Measurements for Pharmacokinetics

Three blood samples (each 350  $\mu$ L) should be collected from all patients. Each patient will be randomly assigned to one of 8 sampling schedules; all 3 samples are to be taken on the same study day. Half of the patients will have samples taken on Study Day 4 and the other half will have samples taken on Study Day 7. If it is not possible to take samples on the assigned Study Day, it is recommended that samples be taken on the following Study Day.

Blood samples will be collected from all patients at the time of peak concentration (immediately after the end of study therapy infusion) and time of trough concentration (approximately 24 hours after the start of study therapy infusion but prior to the next day's dose). In addition, a sample will be collected at an intermediate time between peak and trough times as shown in Table 3-4. Plasma will be separated from blood and sent to a central laboratory for pharmacokinetic testing. The exact time and date of blood sampling should be recorded on the appropriate eCRF.

Table 3-4
Pharmacokinetic Sample Schedule

Sample Schedule	Number of Patients	Study Days	Peak (Sample 1)	Interim (Sample 2)	Trough (Sample 3)	
1	12		Within 5	Between 2 and 4 hr postdose	Within 15	
2	11		minutes after	Between 6 and 8 hr postdose	minutes	
3	11	Day 4 the end of		Between 10 and 12 hr postdose	prior to	
4	11		the 1-hr infusion	Between 14 and 16 hr postdose	Day 5 dose	
5	12		Within 5	Between 2 and 4 hr postdose	Within 15	
6	11		minutes after	Between 6 and 8 hr postdose	minutes	
7	11	Day 7	the end of	Between 10 and 12 hr postdose	prior to	
8	11		the 1-hr infusion	Between 14 and 16 hr postdose	Day 8 dose	
Volume of blood drawn for each PK sample:		350 μL	350 μL	350 μL		

**Protocol/Amendment No.:** 064-02

Weight should be measured within 12 hours prior to the infusion of study therapy on the assigned day of pharmacokinetic blood sampling, and the study therapy dose given on the pharmacokinetic sample day should be adjusted to reflect the most recently measured weight.

If a patient undergoes any procedure that involves collecting CSF while on study therapy, approximately 350  $\mu$ L of CSF should be retained for pharmacokinetic assessments. If available, a baseline (or prestudy) CSF sample should also be retained.

Plasma will be separated from blood and sent to a central laboratory for pharmacokinetic testing. The CSF will also be sent to a central laboratory for pharmacokinetic testing. Procedures for collection, processing, storage, and shipment of pharmacokinetic samples from blood (plasma) and CSF are included in the Administrative Binder.

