#### 1.6 DOSAGE/DOSAGE FORM, ROUTE, AND DOSE REGIMEN

Caspofungin will be administered at 2 mg/kg once daily (with no loading dose).

Amphotericin B deoxycholate will be administered at 1 mg/kg once daily.

Initial dosing with the study medications will be based on the patient's actual body weight (in kg) at the time of study entry. The patient is to be weighed at least weekly during the treatment period. The study medication dose (mg) should be adjusted as the patient's weight increases to maintain the mg/kg dose of the assigned treatment throughout the study treatment period.

Caspofungin and amphotericin B deoxycholate will both be administered intravenously over approximately 2 hours. As these 2 products differ in color, opaque masking will be used over the infusion materials (e.g., infusion syringe and tubing) to ensure adequate blinding of the treatment group.

The duration of study therapy with caspofungin or amphotericin B deoxycholate is variable and dependent on a variety of factors, including (1) the rapidity of a patient's clinical and microbiological response, (2) the patient's general medical condition, and (3)

**Protocol/Amendment No.:** 064-02

the underlying site of *Candida* infection. In general, patients should be treated with study therapy for a minimum of 14 days following the time of documented negative cultures from the site of infection and improvement of any clinical signs and symptoms of invasive candidiasis. Certain sites of infection, including *Candida* endocarditis, meningitis, osteomyelitis/septic arthritis, and endophthalmitis, may warrant a longer treatment course based on the consideration of a variety of relevant factors (see Table 2-1 in Section 2.4.2, Treatment Plan).

**Protocol/Amendment No.:** 064-02

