### Study Drug Preparation

Caspofungin will be administered at 2 mg/kg once daily (with no loading dose). Dosing with caspofungin will be based on the patient's actual weight at the time of study entry.

Caspofungin will be reconstituted/prepared by an unblinded study pharmacist. Appropriate quantities of caspofungin will be diluted with normal (0.9%) saline to achieve a final concentration not to exceed 0.5 mg/mL. For example, for a 1-kg neonate, the daily caspofungin dose is 2 mg, and should be diluted in at least 4 mL. **NOTE:** Dilution of caspofungin in dextrose-containing solutions is contraindicated. The final total volume of infusate is at the discretion of the unblinded pharmacist and should be based on the patient's ability to tolerate the fluid load. However, the final caspofungin concentration should not exceed 0.5 mg/mL. Full guidelines for the preparation of caspofungin study therapy for infusion are provided in the Pharmacy Binder.

Amphotericin B deoxycholate will be administered at 1 mg/kg (per body weight) once daily. Amphotericin B deoxycholate will be reconstituted/prepared by an unblinded study pharmacist. Dosing with amphotericin B deoxycholate will be based on the patient's actual weight at the time of study entry. The amphotericin preparation will also be administered as a single daily infusion. Full guidelines for the preparation of amphotericin B deoxycholate study therapy for infusion are provided in the Pharmacy Binder

In order to verify the patient is receiving the correct dose of either caspofungin or amphotericin B deoxycholate, weight should be measured at least once weekly while the patient is on study therapy, and the dose of caspofungin or amphotericin B deoxycholate should be adjusted accordingly.

All study therapy (caspofungin or amphotericin B deoxycholate) will be administered intravenously as a single daily dose. Each infusion should be administered over approximately 2 hours. The IV line should be flushed thoroughly after each study therapy infusion. Infusion of study therapy may be given through either a pediatric syringe pump or ambulatory pump if this will help ensure that the patient receives the complete dose.

As these 2 products differ in color, opaque masking will be used over the infusion materials (e.g., infusion syringe and tubing) to ensure adequate blinding of the treatment

**Protocol/Amendment No.:** 064-02

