#### 2.7 PHARMACOKINETIC MEASUREMENTS

Three blood samples (each 350  $\mu$ L) for pharmacokinetic assessments will be collected from all patients. Each patient will be randomly assigned to one of 8 sampling schedules; all 3 samples are to be taken on the same study day. Half of the patients will have samples taken on Study Day 4 and the other half will have samples taken on Study Day 7. If it is not possible to take samples on the assigned Study Day, it is recommended that samples be taken on the following Study Day.

Blood samples will be collected from all patients at the time of peak concentration (within 5 minutes after the end of study therapy infusion) and time of trough concentration (approximately 24 hours after the start of study therapy infusion but prior to the next day's dose). In addition, a blood sample will be collected at an intermediate time between peak and trough times as shown in Table 3-4, in Section 3.3.2.

Weight should be measured within 12 hours prior to the infusion of study therapy on the assigned day of pharmacokinetic blood sampling, and the study therapy dose given on the pharmacokinetic sample day should be adjusted to reflect the most recently measured weight.

If a patient undergoes any procedure that involves collecting CSF while on study therapy, approximately 350-µL of CSF should be retained for pharmacokinetic assessments. If available, a baseline (or prestudy) CSF sample should also be retained.

Plasma will be separated from blood and sent to a central laboratory for pharmacokinetic testing. The CSF will also be sent to a central laboratory for pharmacokinetic testing. Procedures for collection, processing, storage, and shipment of pharmacokinetic samples from blood (plasma) and CSF are included in the Administrative Binder.

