Study therapy administration: During the study therapy period, the study drug (either caspofungin or amphotericin B deoxycholate) will be prepared by the unblinded pharmacist as outlined in Section 2.4.2 (Treatment Plan). All study therapy (caspofungin or amphotericin B deoxycholate) will be administered intravenously as a single once-daily dose. Each infusion should be administered over approximately 2 hours. The IV line should be flushed thoroughly after each study therapy infusion. Infusion of study therapy may be given through either a pediatric syringe pump or ambulatory pump if this will help ensure that the patient receives the complete dose. As these 2 products differ in color, opaque masking of the infusion materials (e.g., infusion syringe and tubing) will be used to ensure adequate blinding of the treatment group. The unblinded pharmacist will be responsible to cover the infusion materials with opaque masking. Importantly, the unblinded pharmacist will not be involved in any of the postinfusion evaluations for the patient. All study personnel involved with the postinfusion evaluations of safety and efficacy outcomes, including the study coordinator(s), investigator, or subinvestigator(s), must have no access to the treatment group assignment or the preparation of the study infusion. Additional details on study therapy preparation are included in the Pharmacy Binder.

Of note, total parenteral nutrition (TPN) can be administered to patients enrolled in this study. However, it is preferred that TPN is not infused through the same intravenous line as the study therapy. For those patients with catheters containing multiple lumens, study therapy should be administered via a separate lumen than the lumen used for TPN infusion. For patients with single lumen catheters as the only intravenous access site, TPN should be held during the 2-hour infusion of study therapy. In this case, the IV line should be flushed thoroughly prior to and following study therapy infusion.

- Blood for laboratory safety tests: Selected hematology and blood chemistry tests from blood will be performed on Day 4 (± 1 day) and Day 7 of study therapy, twice weekly thereafter (while on study therapy), and on the last day of study therapy. The selected laboratory tests for safety evaluation are outlined in Appendix 6.1. The results, which will be tested locally, should be recorded on the appropriate eCRF.

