# 3.5.4.1 Efficacy/Pharmacokinetic Endpoints

#### 3.5.4.1.1 Pharmacokinetic Endpoints

Pharmacokinetic (PK) profile ( $C_{max}$  [peak],  $C_{24 hr}$  [trough]) of the administered dose of caspofungin will be determined for neonates and infants less than three months of age on

**Protocol/Amendment No.:** 064-02

or around Days 4 and 7 of study therapy. Pharmacokinetic profiling will be the responsibility of the Drug Metabolism department of the SPONSOR (or its designee).

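### Table 3-4 times the peak PK sample to the end of a 1-hour infusion, while the rest of the protocol infuses over about 2 hours and leaves *postdose* undefined

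*Combined protocol and SAP*

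**What the plan says.** Three sections give the length of the study-drug infusion in agreement with one another:

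- Section 1.6: "Caspofungin and amphotericin B deoxycholate will both be administered intravenously over approximately 2 hours".
- Section 2.4.2, Study Drug Preparation: "Each infusion should be administered over approximately 2 hours".
- Section 3.2.3.5.1 repeats this and adds, for infants with a single-lumen line, that "TPN should be held during the 2-hour infusion of study therapy".

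Table 3-4 in Section 3.3.2 differs. Its peak column asks for a draw no later than 5 minutes after the end of "the 1-hr infusion", in both the Day 4 block and the Day 7 block.

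The running text on the peak gives no duration. Section 2.7 says "within 5 minutes after the end of study therapy infusion", and Sections 3.2.3.5.1 and 3.3.2 say "immediately after the end of study therapy infusion".

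For schedules 1 and 5, Table 3-4 sets the interim sample at "Between 2 and 4 hr postdose". It does not say whether the clock starts at the beginning or the end of the infusion. The trough in the same section is counted from the start.

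Section 3.5.4.1.1 names two PK parameters, Cmax (peak) and the 24-hour level (trough), and says that the profile "of the administered dose of caspofungin will be determined for neonates and infants less than three months of age".

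**The concern.** Table 3-4 is the only place where the eight randomly assigned sampling schedules are set out, and the text sends sites to it for the interim times. Its infusion length contradicts the treatment sections. A site holding both has two ways to go wrong: it can treat 1 hour as the time of the draw, or it can treat 1 hour as the infusion length for the PK day. In the first case the sample is taken during a 2-hour infusion. In the second, the same dose goes in faster and the end-of-infusion level belongs to a different regimen from that of other patients. Both results would be recorded as a peak.

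Section 3.1.2 supports the dose partly by noting that peak levels stayed within adult clinical experience. A sample taken too early would understate that peak. Each infant gives only three plasma samples, all on one day, so a mistimed sample cannot be made up from other draws.

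The undefined *postdose* adds a smaller problem: on one reading, the earliest interim window starts when the peak sample is due.

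**Working it through.** **Inputs.** Infusion length: 1 hour (Table 3-4) or about 2 hours (Sections 1.6, 2.4.2, 3.2.3.5.1). Peak tolerance: 5 minutes (Section 2.7, Table 3-4). First interim window: 2-4 hours (Table 3-4, schedules 1 and 5). Schedule sizes: 12, 11, 11, 11 on each day (Table 3-4). Allocation 2:1 and about 90 patients (Section 1.5).

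**1. The table's own counts.** 12 + 11 + 11 + 11 = 45 per day, and 45 + 45 = 90. This matches the planned total and the half-and-half split by day, so the table is otherwise coherent.

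**2. Time of the peak draw, in minutes from the start (infusion length + 0 to 5).**

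| Reading | Peak draw |
|---|---|
| 1-hour infusion | 60-65 |
| 2-hour infusion | 120-125 |

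If the 60-65 minute draw is applied to a 2-hour infusion, it falls 55-60 minutes before the end.

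**3. Share of the dose delivered by then, at a constant rate.** 60/120 = 50%, and 65/120 = 54%.

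**4. Effect on the measured level (illustration only).** The documents give no half-life, so I assume 6 to 15 hours, one compartment, steady state, 24-hour dosing and infusion length T = 2 h, with k = ln 2 / half-life. For t up to T, the concentration relative to the end of infusion is

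[(1 − e^(−kt)) + (1 − e^(−kT)) · e^(−k(t + 24 − T)) / (1 − e^(−24k))] ÷ [(1 − e^(−kT)) / (1 − e^(−24k))]

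- Half-life 6 h, t = 60 min: 0.566
- Half-life 15 h, t = 65 min: 0.715

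A draw on the 1-hour clock would therefore read about 57-72% of the end-of-infusion level under these assumptions.

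**5. First interim window, in hours after the end of infusion.**

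| *Postdose* counted from | 1-hour infusion | 2-hour infusion |
|---|---|---|
| Start | 2 − 1 to 4 − 1 = 1-3 | 2 − 2 to 4 − 2 = 0-2 |
| End | 2-4 | 2-4 |

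The window meets the peak draw in only one cell: start of infusion, 2 hours. The later windows stay clear; counted from the start, the next one opens 6 − 2 = 4 hours after the end of a 2-hour infusion.

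**6. Patients in that window.** Schedules 1 and 5: 12 + 12 = 24 of 90 (27%). At 2:1, 24 × 2/3 = 16 are on caspofungin, if schedules are balanced across arms.

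**7. How much of the window overlaps.** 5 minutes of 120 = 4%. If draws were spread evenly over the window (assumption), 24 × 5/120 = 1 patient would be sampled inside the peak tolerance.

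**The case against.** A reader might infer that following Table 3-4 literally means drawing the peak during the infusion. The documents do not support that. The cell itself, like Sections 2.7, 3.2.3.5.1 and 3.3.2, ties the draw to the end of the infusion. A site that waits for the end of a 2-hour infusion complies with all of them apart from the stated length. The early draw needs a site to read 1 hour as a clock time.

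A reader might also infer that the 24 patients on schedules 1 and 5 are left with about two distinct time points. That does not follow either. The overlap requires *postdose* to run from the start of infusion. The trough wording favours that reading, but Section 3.1.2 describes the Protocol 058 samples both as post-infusion and as post-dose, which points the other way. Even on a start clock, only the opening edge of the window meets the peak, and the text asks for an interim time between peak and trough.

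Three further points stand. PK is not among the primary or secondary objectives, and no PK hypothesis is tested. Exact sample times go on the eCRF, so an early draw could be detected. Collection procedures are also in an Administrative Binder that is not available here.

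These points limit the consequences but leave the conflict between the sections. A recorded sample time shows whether a draw preceded the end of infusion only if the infusion times are known, and the PK sampling paragraphs in Sections 3.2.3.5.1 and 3.3.2 do not mention recording them. Detecting an early draw does not turn it into a Cmax.

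**Conclusion.** The inconsistency is certain and confined to Table 3-4, where it appears in both day blocks. The 1-hour sampling times in Section 3.1.2 belong to Protocol 058 and were counted after infusion, so they do not support a 1-hour infusion here.

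The consequences are conditional. If a site takes the table as a 1-hour clock, the draw comes 55-60 minutes before a 2-hour infusion ends, with 50-54% of the dose delivered. The 57-72% figure for the measured level rests on the assumed half-lives. If a site changes the infusion length on the PK day, its Cmax reflects a different input rate. The documents do not show how many sites would do either.

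The interim-window problem holds only if *postdose* runs from the start of a 2-hour infusion. It then concerns 24 of 90 patients (about 16 on caspofungin), at the opening edge only.

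This should be corrected because it affects the consistency of a named PK parameter. It does not affect fungal-free survival, the sample size or the safety comparison.

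**What to change.** 1. Reconcile the infusion length in Table 3-4 with Sections 1.6, 2.4.2 and 3.2.3.5.1. Which duration is correct is for the sponsor to settle; the passages must agree.
2. Define *postdose* in Table 3-4 as counted from the start or from the end of infusion, so that the first interim window opens after the peak draw has been taken.
3. Record the actual start and stop times of the infusion on the PK day beside the sample times already required, unless the Administrative Binder or eCRF already provides for this.

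The cost is a correction to one table, matching site instructions and, if needed, two time fields on the eCRF. No additional blood draws are required.

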# 3.3.3 Microbiological Measurements

In addition to local microbiological testing, identification and susceptibility testing will be performed at a central laboratory contracted by Merck on the following isolates: (a) *Candida* isolates collected at study entry, (b) at any time subsequent fungal isolates are obtained, and (c) at any time that there is clinical or laboratory evidence of persistence or progression of the infectious process. The investigator should ensure that the *Candida* isolate(s) obtained from the invasive site of infection at these time points are saved and sent to the fungal isolate central laboratory.

Procedures for collection, processing, storage, and shipment of microbiological samples from blood (plasma) and other non-blood sites of *Candida* infection are included in the Administrative Binder.

#### 3.3.4 Data Monitoring Committee

The Data Monitoring Committee (DMC) is a group with pertinent expertise that reviews on a regular basis accumulating safety data during the study to assess the effects of the study drug. With the exception of a non-voting SPONSOR (or designee) statistician, the members of the committee are independent of the SPONSOR and clinical investigators participating in the trial, and will not have any other involvement in the study, nor will they have any relation to the study participants. The statistician role may alternatively be filled by an individual external to the SPONSOR (or its designee).

To guarantee the unbiased performance of its task, the DMC will initially receive blinded study data from the designated statistician. If required to address a safety concern, unblinded safety data may be requested by and provided to the DMC.

Prior to scheduled meetings, the DMC will be provided with the following reports, which are cumulative and generated from a current data file:

- Patient enrollment status, including counts of patients enrolled by study site
- Blinded counts tables of all adverse events (AEs), drug-related AEs, serious AEs, drug-related serious AEs, and AEs leading to discontinuation
- Blinded counts tables of clinically significant laboratory AEs

**Protocol/Amendment No.:** 064-02

The need for additional reports will be assessed once the DMC members have been appointed and the study is initiated. Unblinded data may be provided to the DMC by the SPONSOR (or its designee) upon request.

Based upon review of the accumulating safety data, the DMC will recommend if the study should continue, be modified, or terminated for safety reasons. The DMC may also recommend steps needed to ensure the safety of study participants and integrity of the trial or trial data. Guidelines for making such recommendations will be developed by the SPONSOR (or its designee) and DMC in advance of the evaluation of study data by the DMC. Following each meeting, the DMC Chairperson will be responsible for reporting post-meeting decisions and/or recommendations (e.g., discontinuation of study due to a major safety concern) to a steering committee comprised of Merck Senior Management members (Merck Senior Management Committee, or MSMC). It will be the responsibility of the MSMC to carefully consider and appropriately implement the recommendations of the DMC and to ensure the investigators and the respective Institutional Review Boards (IRBs)/Independent Ethical Committees (IECs) are properly notified. The MSMC will inform the protocol team of any modifications to the protocol. The investigator, study site staff, and blinded SPONSOR personnel will remain strictly blinded to specific patient treatment group assignments until the study has ended.

Further details regarding the DMC and its functions will be described in the DMC Charter.

